12.2. Additional Details on Study Visits

12.2.1. Screening/Baseline

For ERT-experienced subjects, the Screening Visits will be scheduled on approximately Day -30 and/or Day -15, 1 to 4 days before the subject's next alglucosidase alfa infusion. For ERT-naïve subjects, the Screening Visit may be scheduled any time before Day -10. The Screening Visit will occur over 2 or more days to allow for repeated 6MWT and pulmonary function test assessments. The repeated tests for 6MWT or for pulmonary function (FVC, SVC, MIP, and MEP, and SNIP) should not be done on the same day. No other assessments should be performed on the day that the 6MWT and pulmonary function tests are repeated.

The informed consent form (ICF) must be signed before any study procedures are performed. Subjects will then be registered using IRT.

Subjects who meet eligibility criteria at screening will be randomly assigned to study drug using IRT at least 10 days prior to the first scheduled infusion on Day 1 to allow sufficient lead time for the first drug shipment. All subsequent shipments will be sent automatically through IRT. Refer and comply with detailed guidelines in the IRT manual. The subject does not have to be present for randomization.

Baseline efficacy assessments will be performed during screening. The average of the 2 screening 6MWDs will be the baseline 6MWD value. For FVC, the higher of the 2 screening values will be the baseline value, and baseline values for all other pulmonary function tests (SVC, MIP, MEP, and SNIP) will be those obtained at the same visit during which the higher value for FVC was obtained.

Subjects who fail to qualify for the study may be rescreened up to 2 times in consultation with the Amicus medical monitor, with the following exception regarding inclusion criterion #7 (see Section 9.2.1).

If a subject fails inclusion criterion #7, then the 2 screening 6MWTs may be repeated within approximately 2 weeks from the initial screening visit if, in the opinion of the investigator, the subject is considered likely to meet this criterion on a second attempt. If either screening 6MWD is $\geq 90\%$ of the predicted value for healthy adults (calculated automatically using IRT [Enright, Sherill 1998]), that subject will not be permitted to repeat the 6MWTs or rescreen at a later date.

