15.3.2.3. Efficacy Analyses

For functional assessments, screening results will serve as the baseline values. For 6MWD, the 2 values for 6MWD obtained at screening will be averaged to get the baseline value. For FVC, the higher of the 2 screening values will be the baseline value, and baseline values for all other pulmonary function tests (SVC, MIP, MEP, and SNIP) will be those obtained at the same visit during which the higher value for FVC was obtained.

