2. INTRODUCTION

This statistical analysis plan (SAP) describes the planned data derivations, analyses, and statistical methods to be performed for Study ATB200-03. It is based on:

- Protocol for ATB200-03 Amendment 3 dated 14 August 2020
- Amicus standard operating procedure (SOP) ATCRA-SOP-AT-008
- Good Clinical Practices (GCP) and International Conference on Harmonisation (ICH) guidelines E9 (Statistical Principles for Clinical Trials)
- Discussions with Regulatory Authorities

The purpose of this document is to provide details on study populations and on how the variables will be derived, how missing data and intercurrent events will be handled, as well as details on statistical methods to be used to analyze the efficacy and safety data from Study ATB200-03.

The document may evolve over time to reflect protocol amendments, regulatory discussions, and other important changes. However, the final SAP will be finalized, approved by the Sponsor, and placed on file before the database is locked. The data analyses and statistical methods specified in the final SAP supersede those described in the study protocol. Deviations from the final approved plan will be noted in the clinical study report.

Pharmacokinetic (PK) and immunogenicity analyses will be covered in separate analysis plans.

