6.2.2. Baseline Definition

In general, baseline is defined as the last non-missing measurement prior to the administration of the first dose of study drug, unless otherwise specified. It is understood that baseline may be different for different efficacy and safety endpoints.

- For the 6MWD, FVC, and SVC, the average of the last 2 values obtained on or prior to the first dose date will be used as the baseline value.
- For other functional assessments (such as the MMT, QMT, TUG, GSGC, PROMIS instruments, EQ-5D-5L (quantitative EQ-VAS score and descriptive health status), and R-PAct scale), the screening results will serve as the baseline values.
- For all other pulmonary function tests (MIP, MEP, and SNIP), baseline will be the last available value obtained on or prior to the first dose date.
- For safety data (including all lab assessments, physical examinations, ECG, vital signs, weight, etc), the last available result on or prior to the first dose date will be used as the baseline value (without considering the time of assessment on Day 1). If this value is missing, then the screening value will be used instead.

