8.6. Analysis of the Key Secondary Endpoints

Key secondary endpoints will be analyzed according to the hierarchical order specified in Section [8.3.2](#) using a stepwise closed testing procedure to control the overall Type 1 error rate.

Each key secondary endpoint will be analyzed using an ANCOVA model on the ITT-LOCF population. The model will be adjusted for the baseline value (as a continuous covariate) and ERT status (ERT-naïve versus ERT-experienced), as well as baseline age, gender, baseline height, and baseline weight to compare between the 2 treatment groups. The OBSMARGINS (OM) option in the LSMEANS statement will be specified to allow for the use of the observed marginal distributions of the categorical variable rather than assuming a balance among the levels of the categorical variable. The E option will also be specified to check for estimability of LS means. If the LS means are not estimable with the OM option but they are without it, then the analysis without the OM option will be used.

All the relevant estimates from the ANCOVA (including LS means for each treatment group, LS mean difference, standard error of the estimate, 95% CI for the LS mean difference, and p-value for comparing between the 2 treatment groups) will be provided.

The treatment-by-covariate interactions (ie, treatment-by-ERT status, treatment-by-baseline value, treatment-by-age, treatment-by-gender, treatment-by-weight, and treatment-by-height) will be explored. Each interaction term will be explored using a separate ANCOVA model that includes the full set of covariates (ie, treatment, baseline value (as a continuous variable), ERT status, baseline age, gender, height, and weight) as well as the interaction term. Interaction terms with a 2-sided $p < 0.10$ will be further examined clinically. Forest plots will be used to present

the subgroups defined by the baseline covariates. A plot of the LS mean (\pm SE) change from baseline over time will be provided for each key secondary endpoint.

As a supportive analysis, each of the key secondary endpoints will be analyzed using an MMRM analysis on the ITT-OBS population. See further description in Section 8.5.1.1.

For the % predicted FVC, additional supportive and sensitivity analyses will be performed as specified in Section 8.5.1.1 and Section 8.5.1.2, respectively.

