8.8.3. Other Pulmonary Function Tests

The other pulmonary function test endpoints (ie, % predicted SVC, maximum VC [% predicted], % predicted MIP, % predicted MEP, and SNIP [% predicted]) will be summarized by treatment group and visit. In addition, the change from baseline to Week 52 for each endpoint will be analyzed and compared between the 2 treatment groups using an ANCOVA model on the ITT-LOCF population, similar to that for the key secondary endpoints. No sensitivity or supportive analyses will be conducted for these.

A plot of the LS mean (\pm SE) change from baseline over time will be provided for the pulmonary function test (PFT) endpoints by treatment group. In addition, the difference between sitting FVC and supine FVC results will be summarized by visit.

The % predicted SVC will be calculated as: $(\text{observed SVC results} / \text{predicted value}) * 100$, where the predicted value is obtained from the corresponding VCMax predicted value in the dataset

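### SAP 6.2.2 takes one of two screening values as baseline for MIP, MEP and SNIP but averages both for 6MWD, FVC and SVC, losing a little precision on three other secondary endpoints

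*SAP*

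**What the plan says.** **Measurement.** Protocol Table 10 marks MIP, MEP and SNIP at Screening 1 and Screening 2, the same pattern as FVC and SVC, and does not mark them on Day 1. Protocol 12.2.1 shows that the repeat is deliberate and on separate days: "The repeated tests for 6MWT or for pulmonary function (FVC, SVC, MIP, and MEP, and SNIP) should not be done on the same day".

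**Protocol baseline rule.** Section 12.2.1 takes the higher of the two screening values for FVC and then states "baseline values for all other pulmonary function tests (SVC, MIP, MEP, and SNIP) will be those obtained at the same visit" as that higher FVC. Section 15.3.2.3 repeats the rule: the values "will be those obtained at the same visit during which the higher value for FVC was obtained".

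**SAP baseline rule.** Section 6.2.2 uses "For the 6MWD, FVC, and SVC, the average of the last 2 values obtained on or prior to the first dose date". For the other pulmonary tests it says "MIP, MEP, and SNIP), baseline will be the last available value obtained on or prior to the first dose date". Since none is scheduled on Day 1, that will ordinarily be the Screening 2 value.

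**Precedence.** SAP Section 2: "The data analyses and statistical methods specified in the final SAP supersede those described in the study protocol". The last-value rule is therefore the operative one.

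**Use in the analysis.** SAP 3.3.3 lists % predicted MIP, MEP and SNIP at Week 52 among the other secondary endpoints. Section 8.8.3 analyses each with an "ANCOVA model on the ITT-LOCF population, similar to that for the key secondary endpoints. No sensitivity or supportive analyses will be conducted for these". The model it points to, in Section 8.6, is described thus: "The model will be adjusted for the baseline value (as a continuous covariate) and ERT status", with age, gender, height and weight added.

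**The concern.** Five repeated pulmonary measures come from the same two screening days. The SAP averages two of them and takes a single reading for the other three, without giving a reason. The protocol had grouped SVC with the pressures. In replacing the protocol rule, the SAP moved SVC to averaging and the pressures to the last value.

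The baseline enters each analysis twice: it is subtracted to form the change score, and it is the continuous covariate. Measurement error in a single reading weakens the covariate's correlation with the Week 52 value and so leaves more residual variance. What is at stake is the width of the confidence intervals for three pressure endpoints. No supportive or sensitivity analysis is planned for them, so no other planned analysis would use the second reading.

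**Working it through.** **The plan's own figure.** The plan states no power, SD or reliability for MIP, MEP or SNIP. Its only power figure is for 6MWD (SAP 4.3): 66 vs 33 subjects, standardized effect 0.7, one-sided 0.025. The noncentrality is 0.7/√(1/66 + 1/33) = 3.28 on 97 df, which gives 90.2% against the stated figure of about 90%. It reproduces, and this point does not touch it.

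**Inputs.** From the documents: two scheduled screening values, one of them used; ANCOVA with baseline as covariate. Assumed, because the documents are silent: test-retest ICC ρ from 0.70 to 0.95, and true-score correlation r between baseline and Week 52 from 0.80 to 0.95.

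**Formulas.** Set the variance of a single reading to 1 at baseline and at Week 52, with the same ρ at both. With baseline as covariate, the treatment estimate is the same whether the response is the change or the Week 52 value, so the Week 52 residual variance is what matters.

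- Single baseline: the correlation with Week 52 is ρr, so residual variance = 1 − ρ²r².
- Mean of two: baseline reliability is 2ρ/(1+ρ), so residual variance = 1 − 2ρ²r²/(1+ρ).
- SE ratio = √(mean of two / single).

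**Worked case, ρ = 0.80, r = 0.90.** ρ²r² = 0.64 × 0.81 = 0.5184. Single: 1 − 0.5184 = 0.482. Mean of two: 1 − 1.0368/1.80 = 0.424. Variance ratio 0.880, SE ratio 0.938. Since 99 × 0.880 ≈ 87, about 87 subjects with averaged baselines match the precision of 99 with single ones.

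**SE ratio over the assumed range**

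| ρ | r = 0.80 | r = 0.90 | r = 0.95 |
|---|---|---|---|
| 0.70 | 0.959 | 0.940 | 0.927 |
| 0.80 | 0.961 | 0.938 | 0.921 |
| 0.90 | 0.971 | 0.948 | 0.926 |
| 0.95 | 0.982 | 0.965 | 0.942 |

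The SE falls by 1.8% (ρ = 0.95, r = 0.80) to 7.9% (ρ = 0.80, r = 0.95). The matching variance ratios are 0.965 and 0.848, a reduction of about 4% to 15%. The formula ignores the other covariates and missing data, so it is a guide to size only.

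**When averaging would not help.** With error variances e₁ and e₂ for the first and second readings, the mean has error variance (e₁ + e₂)/4. That is below e₂ unless e₁ exceeds 3e₂.

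**The case against.** The strongest reply is that this is a choice between valid rules. SAP 6.2.2 opens with the last non-missing pre-dose value as its general definition and accepts that baseline may differ between endpoints. On that reading the pressures follow the default and 6MWD, FVC and SVC are the exceptions. There is also a plausible context, though it is an inference: FVC is the first key secondary endpoint, and SVC is tied to it because maximum VC is the larger of the two (SAP 3.3.3). The protocol also used a single value for the pressures, so the SAP changes which visit counts and drops no measurement that the protocol would have used. All of this stands, and it makes the point one of efficiency.

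A second reply is practice: if subjects improve between screening days, the later reading may lie nearer to pre-treatment status. The SAP does not argue this, and the same reasoning would apply to the 6MWD and FVC values that it averages. A shift common to both arms does not bias the adjusted difference. It does move the descriptive within-arm change: if the mean rises by δ between the readings, the averaged baseline is δ/2 lower than the last value and the reported change is δ/2 larger, equally in expectation in both arms.

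Two stronger readings are tempting. A reader might infer that leaving out one of the two readings makes these analyses invalid or biased. The documents do not support that: the rule is pre-specified, applies to both arms alike, and sits in a randomized comparison. A reader might also put the gain at 20% of variance and 10% of SE by taking 0.80 both for test-retest and for the observed correlation between baseline and Week 52. With equal reliability at Week 52, that implies a true-score correlation of 0.80/0.80 = 1.0, meaning that subjects' relative standing does not change over a year on two treatments in a mixed ERT-naïve and ERT-experienced population. Nothing in the documents supports that corner.

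**Conclusion.** The inconsistency is real and the SAP does not explain it: two documents give three baseline rules for measurements taken on the same two days, and the operative rule uses one of two available readings for MIP, MEP and SNIP. The consequence is small. The last-value rule is valid and unbiased, and it costs an estimated 2% to 8% in the SE of the treatment difference. That range rests on the assumed ICC and correlation and on the two readings being exchangeable apart from a common shift. It concerns three endpoints that SAP 8.4 leaves outside error control. They are not in the key secondary hierarchy (8.3.2) or the composite response (8.7). Sample size, alpha and the power for 6MWD are unchanged. This is an improvement worth making, not a defect that threatens a conclusion.

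**What to change.** In SAP 6.2.2, before database lock:

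- Add MIP, MEP and SNIP to the bullet that averages the last two values on or before the first dose date, and delete their separate bullet.
- State that where only one such value exists, it is used.
- Note that this departs from the higher-FVC-visit rule in Protocol 12.2.1 and 15.3.2.3.

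The cost is a few lines of text and a small programming change; no new data are needed. The one downside is the slight shift in descriptive within-arm change if there is a practice effect between screening days. If the sponsor prefers to keep the last value, one sentence giving the reason and acknowledging the change from the protocol would settle the inconsistency, though not recover the precision.

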Subjects who sign an ICF but fail to qualify for the study will be considered screen failures. The reason for not being started on study drug will be entered into the electronic data capture system. The demographic information, informed consent, and Inclusion/Exclusion pages must be completed for subjects who are considered screen failures. Subjects who are rescreened after 1 month must re-sign the ICF and re-perform all screening assessments. For those subjects who had already undergone the confirmatory *GAA* genotyping as part of the previous screening procedures, no repeat *GAA* genotyping is required. Instead, the results of *GAA* genotyping can be used to determine subject's eligibility during the rescreening process.

12.2.2. Day 1

Day 1 is the first day of study drug administration. All study assessments will be performed predose and results from this visit will serve as baseline for safety assessments.

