12.2.3. Infusion Visits and Home Infusion Visits

Infusion visits will be scheduled every 2 weeks for administration of study drug. Changes in the protocol-prescribed duration of study drug infusion due to safety or tolerability issues will be documented in the eCRF. In addition to the assessments noted in [Table 10](#), each site should follow their facility guidelines for performing infusions to monitor vital signs or other safety procedures that may be in place.

At visits through Week 6, additional safety assessments (eg, clinical laboratory tests) will be performed for monitoring of initial safety. In addition, subjects will be monitored for 3 hours after the end of the first 3 infusions (ie, Day 1 and Weeks 2 and 4) by study personnel who are trained in diagnosing and treating acute hypersensitivity reactions and who have immediate access to medication and equipment to treat such reactions. Any additional monitoring according to standards at individual sites should also be performed. Any signs or symptoms noted during or after the infusion should be reported as an AE. All assessments will be performed before infusion of study drug. No efficacy assessments will be performed at these visits.

If consistent with local laws and regulations, subjects may be considered eligible for administration of ATB200/AT2221 at their home. Eligible subjects may request participation in the Home Infusion Program with requests granted on a case-by-case basis following discussion between the Amicus medical monitor and investigator with prior approvals from IRBs/IECs/REBs and regulatory authorities. Home infusions of ATB200 will be performed by a trained home infusion nurse provided by an Amicus designated home infusion service provider. All subjects participating in the Home Infusion Program will be required to complete all functional assessments at the protocol-specified site visits.

Subjects who participate in the Home Infusion Program must meet all of the following inclusion criteria and none of the following exclusion criteria.

Inclusion Criteria:

- Resides in a country where it is permissible to administer alglucosidase alfa outside of a hospital setting
- Meets the following requirements regarding feasibility of the home site for ERT infusion:
 - Availability of sufficient space to prepare and administer ATB200 infusion
 - Availability of utilities and equipment required for storage of study drug upon receipt

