12.3.12. Clinical Laboratory Tests

12.3.12.1. Chemistry, Hematology, and Urinalysis

Clinical laboratory tests for safety monitoring include serum chemistry (Table 11), hematology (Table 12), and urinalysis (Table 13). Clinical laboratory tests will be performed prior to administration of study drug. The collection, processing, and shipment of all biological samples will be fully described in the study laboratory manual.

The investigator (or his/her designee) will review each laboratory report from the central laboratory and assess any out-of-range laboratory results as “not clinically significant” or “clinically significant” (see Appendix 2). Any results that are considered clinically significant should be confirmed in a repeat test at the investigator’s discretion. The investigator should consider repeat testing of persistent clinically significant results until the analyte returns to normal or until an etiology is determined. The investigator (or his/her designee) will sign and date all laboratory reports. Results for CK, ALT, and AST will be blinded to investigators and reviewed by an unblinded medical monitor.

Table 11: Serum Chemistry Parameters

ALT	Creatinine
Alkaline phosphatase	GGT
AST	Glucose
Albumin	LDH
Bilirubin, total	Magnesium
BUN	Phosphorous
Calcium, total	Potassium
Carbon dioxide, total (bicarbonate)	Protein, total
Chloride	Sodium
CK	Uric acid

Abbreviations: ALT = alanine aminotransferase; AST = aspartate aminotransferase; BUN = blood urea nitrogen; CK = creatine kinase; GGT = gamma-glutamyltransferase; LDH = lactate dehydrogenase

Table 12: Hematology Parameters

Platelet count	Automated white blood cell differential:
Red blood cell count	Neutrophils
White blood cell count (absolute)	Lymphocytes
Hematocrit	Monocytes
Hemoglobin	Eosinophils
	Basophils

Table 13: Urinalysis Parameters

Color	Ketones
Appearance	Blood
Specific gravity	White blood cells
pH	Nitrite
Protein	Bilirubin
Glucose	Microscopy of sediment

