12.3.15.2. Pharmacokinetic Subanalysis (ERT-naïve Subjects Only)

A PK subanalysis will be conducted in ERT-naïve subjects. Serial blood samples will be collected just prior to initiation of ATB200/αglucosidase alfa infusion (time 0) and at 1, 2, 3, 3.5, 4, 4.5, 6, 8, 10, and 24 hours after the start of ATB200 infusion for plasma total GAA protein signature peptide T09 and plasma AT2221 determinations. Collection of a 12-hour sample will be optional.

For serial blood sampling on Day 1, the predose (Time 0) PK blood sample should be collected within 30 minutes before the start of ATB200 infusion. The 1-, 2-, 6-, 8-, 10-, and 12-hour PK blood samples should be collected within a ± 15-minute window. The 3-, 3.5-, 4-, and 4.5-hour

PK blood samples should be collected within a \pm 5-minute window. The Day 2, 24-hour PK blood sample should be collected within a \pm 30-minute window.

At Week 52, ERT-naïve subjects will also have sparse blood samples taken at same the time points listed for ERT-experienced subjects (Section 12.3.15.1).

Vital signs may be measured after each PK blood sample for monitoring of safety, as per local clinical guidelines, but results will not be recorded in the eCRF.

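### The safety baseline ignores clock time on Day 1, so an off-schedule post-dose record could become the baseline for change-based safety summaries

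*SAP*

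**What the plan says.** SAP 6.2.2 opens with a default: "baseline is defined as the last non-missing measurement prior to the administration of the first dose of study drug, unless otherwise specified". It adds that baseline may differ between endpoints. For laboratory tests, physical examinations, ECGs, vital signs and weight it then gives a separate rule: "the last available result on or prior to the first dose date will be used as the baseline value", and it qualifies this with "without considering the time of assessment on Day 1". Screening values serve only as a fallback if that result is missing.

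Protocol 12.2.2 ties the same baseline to predose collection: "All study assessments will be performed predose and results from this visit will serve as baseline for safety assessments". Two further protocol sections support predose timing. Section 12.2.3, on the early infusion visits, says "All assessments will be performed before infusion of study drug", and 12.3.12.1 says "Clinical laboratory tests will be performed prior to administration of study drug". Vital signs may be taken after PK samples, "but results will not be recorded in the eCRF" (12.3.15.2, with the same provision in 12.3.15.1).

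**The concern.** A baseline for drug safety should precede the drug. The protocol secures this by requiring predose collection. The SAP bullet replaces that condition with a calendar date, and a calendar date cannot separate a reading taken before the first infusion from one taken after it.

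The subjects most likely to have an extra Day 1 reading are those who became unwell during or after the first infusion. Any misclassification would therefore not be random. It would fall on the subjects in whom acute change matters most, and it would understate that change. At stake are the by-visit change-from-baseline summaries and the incidence of pre-defined limits of change in SAP 9.2, 9.3.1 and 9.3.3. No efficacy result or error rate depends on this rule.

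**Working it through.** The plan gives no figure on this point to reproduce. The check compares the rules and then applies SAP Table 10 to assumed values.

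**1. Which Day 1 records can be post-dose?** Scheduled ones cannot, if the protocol is followed (12.2.2, 12.2.3, 12.3.12.1). Vital signs taken after PK samples do not enter the eCRF. Three sources remain:
- unscheduled or repeat safety tests, which protocol 12.2.5 allows at any time for medical reasons;
- readings from site infusion monitoring under 12.2.3, if they are recorded (the text does not say);
- timing deviations.

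The SAP expects off-schedule records in the data: 6.2.7.2 covers unscheduled safety assessments, 9.2 lists retests and unscheduled laboratory results, and 9.3.3 includes unscheduled ECGs in the limit-of-change summary.

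**2. What does the SAP do with such a record?** Table 4 gives Day 1 only a baseline role, and the first post-baseline window starts on Day 2. The rule in 6.2.7.2 for choosing among several records in a window applies only after baseline. So 6.2.2 alone decides. If time is truly ignored, two records on the same date have no defined order. If they are ordered by time, the post-dose record is the last one and becomes the baseline.

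**3. How does the SAP treat Day 1 elsewhere?** For adverse events, SAP 9.1 uses clock time and counts an event with a missing start time as treatment-emergent. The baseline rule runs the other way: a value known to be post-dose can be treated as pre-treatment.

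**4. Effect on a flag (assumed values, not trial data).** Table 10 flags low systolic pressure when v ≤ 90 and b - v ≥ 20, where v is a post-dose value and b the baseline. Assume 130 mm Hg predose and 85 post-dose on Day 1.

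| Quantity | b = 130 (predose) | b = 85 (post-dose) |
|---|---|---|
| Day 1 post-dose value of 85 | 85 - 130 = -45, flagged | 85 - 85 = 0, not flagged |
| Highest later value that is flagged | lower of 90 and 130 - 20 = 110, so 90 | lower of 90 and 85 - 20 = 65, so 65 |
| Later value of 130 | change 0 | change +45 |

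For this subject, later readings from 66 to 90 would also go unflagged. The spurious +45 does not trigger the high systolic limit, which also needs 180 or more, so it enters only the change-from-baseline summary.

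Pulse behaves the same way. With 80 predose and 125 post-dose, the change is 125 - 80 = +45. This meets the limit of at least 120 with a rise of at least 15. With 125 as baseline the change is 0 and nothing is flagged.

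**5. Scale per affected subject.** With about 110 subjects randomized 2:1, the arms hold about 110 × 2/3 = 73 and 110/3 = 37. If the later value is 130, one such subject shifts the arm's mean change in systolic pressure by 45/73 = 0.6 mm Hg or 45/37 = 1.2 mm Hg. One lost flag lowers an incidence by 1/73 = 1.4 or 1/37 = 2.7 percentage points. The number of such subjects is unknown and may be zero.

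**6. Which limits are affected?** Those with a change component: all of Table 10, the composite and change criteria in Table 9, and the QT change categories in Table 11. Purely absolute limits (ALT and AST multiples, bicarbonate, PR, QRS) do not use the baseline value. A Day 1 post-dose result classed as baseline would, however, not itself count as post-baseline.

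**The case against.** The strongest case against the point is that the rule works as intended for the data the protocol plans to collect. If every scheduled Day 1 assessment is predose, a Day 1 record is a valid baseline whatever its clock time. Ignoring the time then avoids discarding good records because a time is missing or wrong. The main routine source of post-dose vital signs is kept out of the eCRF, and the documents do not show that any post-dose Day 1 safety record exists. Safety analysis is descriptive, with no formal tests (SAP 9). All of this stands, and it limits the point to off-schedule records.

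Two stronger readings are tempting, and the documents support neither.

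- A reader might infer that SAP 6.2.2 contradicts itself. It does not. The default definition allows for exceptions, and the safety bullet is one. What can fairly be said is that the exception gives no reason and does not carry over the protocol's predose condition.
- A reader might infer that an acute reaction would be hidden. It would not. Protocol 13.1.3 requires signs and symptoms during the infusion, or within 2 hours of its end, to be reported as immediate infusion-associated reactions unless there is an obvious alternative cause. SAP 9.1 classifies Day 1 events by clock time. SAP 9.1.3 and 9.1.4.3 summarize the reactions by severity and by time after infusion start. None of this uses the laboratory or vital-sign baseline.

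Listings also give some protection: all laboratory results (9.2) and all ECG data (9.3.3) are listed. Vital signs are less protected, because the listing in 9.3.1 is triggered by a limit-of-change flag, so a masked flag can also remove the readings from that listing.

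**Conclusion.** The point holds in a narrow form. SAP 6.2.2 allows a post-dose Day 1 safety value to serve as baseline, and no other SAP rule prevents it. The consequence is confined to change-from-baseline summaries and to limits that depend on baseline. In an affected subject it can turn a 45 mm Hg fall into no change, as in the assumed example.

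This rests on two conditions that the documents do not settle: that a post-dose value from Day 1 is in the safety database, and that it is taken as the last one that day. If no such record exists, no result changes. The defect is minor, and correcting it is a free improvement.

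**What to change.** Amend the safety bullet in SAP 6.2.2 as follows:

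- Define the safety baseline as the last non-missing value before the date and time of the first dose of study drug.
- If the time is missing on Day 1, accept the scheduled Day 1 record as predose under protocol 12.2.2. Use an unscheduled Day 1 record only if it is shown to be predose. This keeps legitimate predose repeats.
- Count recorded Day 1 post-dose values as post-baseline in the limit-of-change summaries of SAP 9.2, 9.3.1 and 9.3.3.

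The cost is a short wording change before database lock and a small change to the derivation program. No new data are needed: the missing-time rule covers records without a clock time.
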